### **Power and Sample Size Justification:**

The power and sample size calculation is based on FMA scores from our R03 study. A minimal clinically important difference (MCID) range of 4.25-7.25 points has been reported for the FMA with baseline subject standard deviation of 5.7 – 6.3 points. To be conservative, we have assumed the MCID to be 4.25 for the purposes of our power calculations. Based on results from our R03 which included 3 intervention groups, the forced AE+RTP group, voluntary AE+RTP group, and RTP only groups improved on the FMA by a mean of 12.33(4.13), 4.83(4.91), and 4.4(4.87), respectively. In the sample size and power computation, it is assumed that there is an increase of 2\*MCID for the AE+RTP group and 1\*MCID for the RTP only group, along with

statistically significant differences between the groups at EOT. Further, it is assumed that subject SD will remain ~10 points within the group. Based on these assumptions, with n=30 in each of the intervention groups, we will have a .87 power at the 0.05 significance level to detect pairwise group differences equivalent to an effect size of .4. All computations were completed using the PASS 13 program (East Kaysville, Utah).

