**Recruitment and Sample:** Sixty individuals from the Cleveland Clinic Health System (CCHS) and adjacent medical community with chronic stroke and the following criteria for inclusion will be recruited: 1)  $\geq 6$  months following single ischemic or hemorrhagic stroke confirmed with neuroimaging, 2) Fugl-Meyer motor score 24-50 in the involved UE, 3) Ambulatory  $\geq 20$  meters with no more than contact guard assistance, and 4) 18-85 years of age. Exclusion criteria include: 1) hospitalization for myocardial infarction, heart failure or heart surgery within 3 months, 2) cardiac arrhythmia, 3) hypertrophic cardiomyopathy, 4) severe aortic stenosis, 5) pulmonary embolus, 6) significant contractures, 7), anti-spasticity injection within 3 months of enrollment and 8) other contraindication to exercise. The targeted population represents a collective cohort in whom spontaneous recovery is typically no longer occurring, potential exists for significant motor recovery, and risk associated with intensive AE training is minimized. Since our pilot R03 study, we established numerous collaborative relationships in the Cleveland stroke research community and achieved our targeted enrollment of 30 participants over a 21-month period for the current 2-year AHA study. Drs. [name], Chairman of Physical Medicine and Rehabilitation, and [name], neurologist in the cerebrovascular center, have endorsed our work and actively support our recruitment efforts. Based on the proposed criteria outlined above and in detail in Human Subjects section, during the past 12 months  $\sim 1200$  CCHS patients would be eligible for the trial. To address transportation as a potential barrier to participation and adherence, the Cleveland Clinic offers free transportation to those who live within a 15-mile radius of the campus and free parking in an accessible, attached parking garage for those with their own vehicular transportation. Given our history and approach, recruiting 60 participants is feasible and will be accomplished.

[figure not shown]

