### **Data analysis**

**Consideration of Relevant Biological and Sociological Variables:** Participants in both groups will be compared on potentially confounding baseline variables (age, gender, socio-economic status, education, fitness, co-morbidities, degree of hemiplegia, location/type of stroke, side of lesion) to assess the extent of any imbalances across groups. Baseline variables in which there is a clinically important difference between groups may be included as covariates. Participants will also be compared using participation and adherence metrics. While recent evidence has shown that genetic polymorphisms may influence motor recovery following stroke, it is beyond the scope of this project due to cost and lack of expertise to consider these as covariates.

**Analysis of Motor Outcomes (Aim 1):** Motor outcomes for each group will be compared at baseline, mid-treatment, EOT, and EOT+4. The group effect on ARAT, FMA, and WMFT will be estimated using separate linear mixed effects models with a random effect for subject, fixed effects for group, examination time, and baseline value of the outcome. An appropriate covariance structure (e.g.: unstructured, compound symmetric, autoregressive) will be used as determined using Akaike's information criterion. The effects of group, time, and the group-by-time interaction will be assessed for each outcome. To adjust for multiple comparisons, the family-wise error rate will be controlled via Bonferroni-type adjustment required for multiple comparisons. Tukey's and other post-hoc comparisons will be used to explore pairwise differences in main effects of group membership. To further investigate the effect of the intervention group assignment on the various sub-scales of the ARAT, a multivariate analysis of variance will be used along with a separate principle component analysis to study if further dimension reduction is possible in using these two tests in the study. Transformations of the data will be made to achieve normality or other model assumptions. The overall alpha level will be set at 0.05.

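### The planning SD of about 10 FMA points is unlabelled and unsourced, and it conflicts with the plan's other SDs and with its stated power of .87

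*Combined protocol and SAP*

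**What the plan says.** The Power and Sample Size Justification bases the calculation on Fugl-Meyer (FMA) scores and the R03 pilot. It reports an MCID range "with baseline subject standard deviation of 5.7 – 6.3 points", and says that the three R03 groups "improved on the FMA by a mean of 12.33(4.13), 4.83(4.91), and 4.4(4.87), respectively". For the difference, "we have assumed the MCID to be 4.25 for the purposes of our power calculations", with an "increase of 2\*MCID for the AE+RTP group and 1\*MCID for the RTP only group". For the spread, "it is assumed that subject SD will remain ~10 points within the group". It then states that, "with n=30 in each of the intervention groups", power is .87 at the 0.05 level for an effect size of .4. The type of effect size and the sidedness of the test are not given.

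Two other places bear on the SD. Under Approach, Recruitment and Sample, entry requires a "Fugl-Meyer motor score 24-50 in the involved UE". Under Data analysis, Analysis of Motor Outcomes (Aim 1), the mixed model has "fixed effects for group, examination time, and baseline value of the outcome".

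**The concern.** None of the FMA SDs printed in the power paragraph is near 10. The verb *remain* suggests that the SD is already about 10 at entry, which disagrees with the baseline SD given a few lines above and sits badly with a 26-point entry window. The 10 also disagrees with the power it is meant to support.

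The SD decides what 30 per arm can detect. Between the printed change SDs and 10, power for the same 4.25 points runs from above 0.9 to below 0.4. As written, a reader cannot tell which SD the sample size rests on. Someone who corrected the power but kept the 10 would report a figure that does not describe the planned baseline-adjusted analysis.

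**Working it through.** **Inputs.** From the power paragraph: difference 2 × 4.25 − 1 × 4.25 = 4.25 points; n = 30 per arm; alpha 0.05 (two-sided assumed); SD 10; baseline SD 5.7 to 6.3; R03 change SDs 4.13, 4.91 and 4.87. From the eligibility criteria: FMA 24 to 50. From Preliminary Studies: 17 R03 completers in three groups.

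**1. The stated power.** For two equal arms, d = difference/SD and the noncentrality is d × √(n/2) = d × √15. Power is from the noncentral t with 58 df (normal approximation in brackets).

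- 4.25 points with SD 10: d = 0.425, noncentrality 1.65, power 0.37 (0.38).
- Effect size .4 read as Cohen's d: power 0.33 (0.34).
- Effect size .4 read as Cohen's f, so d = 0.8: power 0.86 (0.87). This matches the stated .87, but with 4.25 points it implies SD = 4.25/0.8 = 5.31.
- Solving for .87 with 4.25 points: SD 5.24 by t, 5.33 by the normal approximation.
- SD 10 with the R03 difference 12.33 − 4.4 = 7.93: power 0.86 (0.87). This also comes close, but 7.93 is not the difference that the paragraph says it assumed.

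The stated 4.25 points and SD 10 therefore do not give .87.

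**2. SD 10 as a baseline SD.** An even spread over 24 to 50 has SD 26/√12 = 7.5. A normal distribution centred at 37 with SD 10, cut off at the limits, has SD 6.7. The mathematical maximum is 13, with half the participants at each limit. On a symmetric beta distribution, SD 10 needs shape 0.345, which is U-shaped with about 67% of participants within 5 points of a limit. That is possible but implausible.

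**3. SD 10 as a raw EOT SD.** The window does not bound EOT scores. With baseline SD b, change SD c and baseline-change correlation r (an assumption), the EOT SD is √(b² + c² + 2rbc).

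- b = 5.7 to 6.3 and c = 4.13 to 4.91: 7.0 to 8.0 at r = 0; 8.5 to 9.7 at r = 0.5. Reaching 10 needs r of at least 0.59 (b = 6.3, c = 4.91).
- b = 7.5 (even spread) and c = 4.91: 9.0 at r = 0. Reaching 10 needs r of only about 0.27.

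**4. The SD that the planned model uses.** At a single visit, adjusting for baseline picks the slope β that minimises Var(post − β × baseline). The change score is the special case β = 1, so the residual SD cannot exceed the change SD. On the R03 figures that is 4.13 to 4.91 or less.

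**5. How well the change SD is known.** Group sizes are not given, so equal weights are assumed. The pooled SD is √((4.13² + 4.91² + 4.87²)/3) = √21.63 = 4.65. With 17 − 3 = 14 df, the 2.5% chi-square point is 5.63, and the 95% upper limit is 4.65 × √(14/5.63) = 7.3.

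**6. Power for 4.25 points, n = 30 per arm, two-sided 0.05 (t).**

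| SD | What it is | Power |
|---|---|---|
| 4.13 | smallest R03 change SD | 0.97 |
| 4.91 | largest R03 change SD | 0.91 |
| 5.7 | lower printed baseline SD | 0.81 |
| 6.3 | upper printed baseline SD | 0.73 |
| 7.3 | upper limit of pooled change SD | 0.60 |
| 10 | the plan's input | 0.37 |

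The analysis section calls for Bonferroni-type control, and Aim 1 names both the ARAT and the FMA as primary clinical outcomes. If alpha is split to 0.025 (an assumption), power is 0.85 at SD 4.91 and 0.62 at SD 6.3.

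**The case against.** The strongest defence is that the 10 is never called a baseline SD. The sentence before it concerns group differences at EOT, and EOT scores can leave the entry window. That stands. A reader might infer that the entry criterion rules out an SD of 10, or that the criteria cannot deliver such a sample. The documents do not support this: step 3 shows that a raw EOT SD near 10 needs only a modest correlation if baseline scores are evenly spread.

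A reader might also treat 4.1 to 6.3 as one range of SDs that the plan reports. It is not. The lower part is SDs of change and the upper part is an SD of baseline scores, and the text leaves open whether the baseline figure comes from R03 or from the cited MCID source. A raw-score SD larger than a change SD is not in itself a contradiction.

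A third objection is that too large an SD is conservative. In direction that is right, and the 10 alone does not show an underpowered trial. But the plan applies the word conservative only to the MCID, and its .87 takes no benefit from the larger SD. The 10 may not have entered the power at all or, if the R03 difference was used, the 4.25 points may not have. The paragraph does not say.

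Finally, the R03 SDs are imprecise, and R03's entry criteria are not given. This also stands. It is why 6.3 cannot be offered as a cautious value and why a range is needed.

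**Conclusion.** The point holds in a limited form. The SD of about 10 is unlabelled and unsourced, and it does not fit the printed baseline SD, the printed change SDs or the stated power. For 4.25 points and 30 per arm it gives 0.37, against the stated .87, which needs an SD of about 5.3. It is implausible as a baseline SD. It is possible as a raw EOT SD, but that is not the SD that matters for a model adjusting for baseline.

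This does not show that 30 per arm is too few: at the largest R03 change SD, power is about 0.91. Nor does it show that .87 is secure: at the approximate upper limit of the pooled change SD, power is about 0.60. These figures assume a two-sided test at one visit, equal weighting of the three R03 groups, 14 df, no dropout, and that R03 variability carries over to this trial.

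**What to change.** In the Power and Sample Size Justification:

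- Replace the SD of about 10 with a labelled and sourced SD for the baseline-adjusted FMA comparison, based on the R03 change SDs. If a raw EOT SD is also quoted, label it as such.
- State whether .4 is Cohen's d or f and whether the test is two-sided, and reconcile .4, .87, the 4.25-point difference and the SD.
- Restate power for 4.25 points and 30 per arm as a range: about 0.91 at SD 4.91, 0.81 at 5.7, 0.73 at 6.3 and 0.60 at 7.3. Note that the last is an approximate 95% upper limit from 17 completers.
- Say whether alpha is split across the ARAT and FMA. If it is split to 0.025, give the lower figures (0.85 at SD 4.91 and 0.62 at 6.3).

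The cost is wording and one recalculation; enrollment stays at 30 per arm. The downside is that a single power figure becomes a range that may fall below .87.

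### The stated power of .87 does not follow from its own assumptions: 4.25 points, SD about 10 and 30 per group give about 0.37 at two-sided 0.05

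*Combined protocol and SAP*

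**What the plan says.** All the power inputs stand in the section Power and Sample Size Justification.

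- **Outcome:** "The power and sample size calculation is based on FMA scores from our R03 study".
- **Difference:** "To be conservative, we have assumed the MCID to be 4.25 for the purposes of our power calculations". The AE+RTP group is assumed to gain twice this amount and the RTP-only group once this amount, with the groups differing at end of treatment (EOT).
- **SD:** "it is assumed that subject SD will remain ~10 points within the group".
- **Sample size and result:** "Based on these assumptions, with n=30 in each of the intervention groups", the plan states that "we will have a .87 power at the 0.05 significance level to detect pairwise group differences equivalent to an effect size of .4".

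The section prints two other sets of SDs. The FMA scores come "with baseline subject standard deviation of 5.7" up to 6.3 points. The three pilot groups (forced AE+RTP, voluntary AE+RTP, RTP only) "improved on the FMA by a mean of 12.33(4.13), 4.83(4.91), and 4.4(4.87), respectively", with SDs in brackets.

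The section does not give the sidedness, the test, the effect-size metric (d or f) or a baseline-to-EOT correlation. Under Data analysis, the motor outcomes are analysed with mixed models adjusted for baseline, and "the family-wise error rate will be controlled via Bonferroni-type adjustment required for multiple comparisons". The Outcomes paragraph of Aim 1 names both the ARAT and the FMA as primary.

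**The concern.** The plan presents .87 as the consequence of the assumptions just listed, so it should be reproducible from them. An effect size of .4 looks like 4.25/10 = 0.425, a Cohen's d, but 30 per group gives nowhere near .87 power for a d of that size.

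This paragraph is the only quantitative support for N=60, and the Experimental Overview lists a justified sample size among the elements that ensure rigour. As written, a reader cannot tell whether the trial is sized for 4.25 points, which the plan calls conservative, or for about 8 points. These lead to different readings of a null result. If the analysed SD really is 10, a true 4.25-point benefit would be missed about 63% of the time (1 − 0.37).

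**Working it through.** **Method.** Two-sample comparison at EOT, n = 30 per group, df = 58. The noncentrality is d × √(n/2) = d × √15 = 3.873d, and power comes from the noncentral t. Two-sided 0.05 is assumed because the plan does not state sidedness.

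**1. The plan's own inputs.** Difference = 2 × 4.25 − 1 × 4.25 = 4.25. d = 4.25/10 = 0.425, or f = d/2 = 0.21. Noncentrality = 0.425 × 3.873 = 1.646, against a critical value of 2.002.

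- Two-sided 0.05: power 0.367 (normal approximation 0.377).
- One-sided 0.05: 0.493 (normal 0.500).
- Per-group size needed for .87 at two-sided 0.05: about 106 (normal approximation), not 30.

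The stated .87 is not reproduced.

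**2. What an effect size of .4 can mean.**

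| Reading | d | Points at SD 10 | Power (t) | Power (normal) |
|---|---|---|---|---|
| .4 is Cohen's d | 0.40 | 4.0 | 0.332 | 0.341 |
| .4 is Cohen's f | 0.80 | 8.0 | 0.861 | 0.873 |

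Only the second reading pairs .4 with .87, and it requires nearly twice the stated difference (8.0/4.25 = 1.9).

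**3. A possible source.** The pilot difference between forced AE+RTP and RTP only is 12.33 − 4.4 = 7.93 points. At SD 10, f = 7.93/20 = 0.397 and power is 0.855 (t) or 0.867 (normal). A three-group ANOVA on the pilot means at SD 10 has f = 0.364 and, with 30 per group, power 0.869. The pilot means may therefore have been entered instead of the MCID difference. This is an inference; the plan does not say so.

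**4. What 4.25 points would need for .87.** Power at n = 30 per group, by analysed SD. The 0.025 column assumes alpha split over two primaries, which the plan does not define.

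| Analysed SD | Where it comes from | Two-sided 0.05 | Two-sided 0.025 |
|---|---|---|---|
| 10 | stated assumption | 0.37 | 0.26 |
| 6.3 | baseline SD, upper | 0.73 | 0.62 |
| 5.7 | baseline SD, lower | 0.81 | 0.72 |
| 5.24 | solved for .87 | 0.87 | 0.80 |
| 4.9 | pilot change SD, upper (rounded) | 0.91 | 0.85 |
| 4.13 | pilot change SD, lower | 0.97 | 0.95 |

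At two-sided 0.05, none of the individual SDs printed in the section gives .87.

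**5. Baseline adjustment.** If 10 is the SD of raw scores, the residual SD at EOT is 10 × √(1 − ρ²), with df = 57. Power for 4.25 points is 0.46 at ρ = .5, 0.62 at .7, 0.77 at .8 and 0.87 at .85. Reaching .87 therefore needs ρ of about 0.85, which is not stated.

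The pilot change SDs imply ρ = 1 − s²/(2S²), where s is the change SD and S the score SD. With S = 10, ρ is .88 to .915 and power 0.925 to 0.980. With S = 5.7 to 6.3, ρ is .63 to .79 and power 0.947 to 0.988.

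**6. Detectable difference at SD 10.** Power of .87 needs d = 0.810 at two-sided 0.05, or 8.1 points, and d = 0.889 at 0.025, or 8.9 points.

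**The case against.** The strongest reply is that 0.37 comes from an unadjusted comparison that the trial will not use. The plan specifies a baseline-adjusted mixed model over three post-baseline visits. Averaging those visits at SD 10 under compound symmetry (an assumption) gives 0.83 at a correlation of .70 and 0.875 at .75. The pilot change SDs also point to power above .87 for 4.25 points. This stands as a limit on the conclusion: the documents do not show an underpowered trial. It does not rescue the sentence, because the section refers to differences at EOT and states no correlation.

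Second, other routes lead to about .87 for 4.25 points. The pilot SDs of 4.87 and 4.91 give 0.873 and 0.867 at two-sided 0.025 by normal approximation. An SD of 5.9, inside the printed baseline range, gives 0.867 one-sided at 0.05. Both are correct, so the remark about printed SDs holds only at two-sided 0.05. Neither route uses the SD of about 10 that the plan says it assumed. That several unrelated routes reach .87 also makes the pilot reconstruction weak evidence.

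Third, the alpha split is a separate matter. The family for the Bonferroni-type adjustment is undefined, and Data Variables attaches the primary label only to the ARAT. The 0.025 figures are therefore illustrative.

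Finally, a null result could still be read from its estimate and confidence interval against 4.25 points. The loss lies in the design justification and does not make the result uninterpretable.

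**Conclusion.** The concern holds. The stated .87 contradicts the assumptions it cites: 4.25 points, SD 10 and 30 per group give 0.37 two-sided or 0.49 one-sided at 0.05. The figures .87 and .4 agree with each other only as Cohen's f, which at SD 10 means about 8 points.

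The 0.37 rests on a single EOT comparison with 10 as the analysed SD and two-sided testing. Under other readings of the SD and correlation, power for 4.25 points at two-sided 0.05 reaches about 0.99. The finding is that the power statement is wrong as written and cannot be reconstructed, not that true power is 0.37. Because it is the sole numerical basis for N=60, it must be corrected.

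**What to change.** Keep N=60 and rewrite the power paragraph so that its figures agree. It should state:

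- the group difference actually entered (4.25 points, the pilot difference of 7.93, or another value);
- whether .4 is d or f;
- the test and its sidedness;
- the alpha used, and whether it is before or after any Bonferroni-type split across FMA and ARAT;
- which SD is meant (score, change or baseline-adjusted residual), with the assumed baseline-to-EOT correlation;
- how an SD of about 10 is reconciled with the baseline SD of 5.7 to 6.3 and the pilot change SDs of 4.13 to 4.91.

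Suggested wording: *With n=30 per group, a two-sided test at alpha A, an FMA difference of D points at EOT and an analysed SD of X, power is Y.*

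For D = 4.25, take Y from the SD table in the working. For D = 7.93 and X = 10, Y is about 0.86 at 0.05 and 0.78 at 0.025. In that case, delete the assumption of twice versus once the MCID, or say that it was not the powered difference. If X is 10, add that the difference detectable with .87 power at 0.05 is about 8.1 points.

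The cost is protocol and SAP wording only. The stated power may become less favourable, or it must openly rest on a difference or SD from a 17-participant pilot.

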## Preliminary Studies

Our preliminary study in patients with stroke and larger studies in Parkinson's disease (**NIH R01HD056316, R21 HD056316**) have provided the majority of clinical efficacy data and technology that will be utilized for the proposed project. Cost-effectiveness analyses have not been conducted on prior studies. The primary goals of the stroke study were to determine feasibility and initial efficacy of utilizing two different modes of AE in patients with stroke as a means to promote functional motor recovery. In our R03, patients were randomized to forced-rate aerobic exercise (FE) along with RTP (FE+RTP), voluntary-rate aerobic exercise (VE) along with RTP (VE+RTP) or time-matched RTP only without an AE component. Preliminary data are presented from 17 participants who completed all study-related interventions and testing. Using a more rigorous study design from our R03, we recently achieved our target enrollment of 30 participants for our ongoing AHA study within a 22 month time period. No data from the ongoing AHA study are reported, as the trial remains active.

### Cardiopulmonary Testing is Safe and Effective for Screening

**Individuals with Stroke:** The pre-CPX medical screen and subsequent CPX testing protocol in this proposal was used successfully in all participants in our preliminary studies in determining the safety of individuals with history of stroke and cardiovascular co-morbidities to participate in the study intervention. Both AE groups demonstrated improvements in peak VO2 with the VE+RTP improving by a mean of 2.4 mL/kg/min and the FE+RTP group improving by a mean of 1.3 mL/kg/min.

### Individuals with Stroke can safely exercise at moderate to high aerobic intensity:

Continuous heart rate monitoring was used to ensure participant safety and to monitor compliance. On average, participants in the FE+RTP and VE+RTP groups exercised at mean intensities of 56.5 [ $\pm 15.7\%$ ] and 55.9 [ $\pm 8.7\%$ ] HRR, well above minimum recommendations.

